## **5.0 Number of Subjects**

Two nursing homes will be recruited for comparison of LSB with care as usual. A power analyses for a MANOVA, with 2 groups and 2 dependent variables, was conducted in G\*Power Version 3.1.9.2 [32] to determine a sufficient sample size. Using an alpha ( $\alpha$ ) of .05, and a large effect size of  $d = .94$  [33], a sample size of 20 could achieve a power of 95% to detect between group differences.

Prior research in long-term care facilities indicates that oversampling by 15-20 percent is an efficient way to deal with attrition. This study will recruit 24 residents, or 12 residents per NH, to ensure a sample size of 20. From these two NHs, a minimum of 20 NH residents (10 per NH) and a maximum of 24 NH residents (12 per NH) will be recruited.

**FULL PROTOCOL TITLE:** The Effectiveness of Life Story Book on Depression and Meaning in Life for Mentally Alert Residents of Nursing Homes

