**Geriatric Depression Scale (Residential) (GDS-12R)** is a shortened version of the 30item Geriatric Depression Scale which has been shown to effectively distinguish depressed from non-depressed older adults [43]. In 1986, a short form of 15-items (GDS-15) was developed for older adults, from the original 30-item questionnaire, primarily for brevity and for use with older adults with health issues or those with dementia. It was found to have a high correlation with depressive symptoms in previous validation studies [44]. Three items were found to not be reflective of residents of nursing homes and these three were omitted from the GDS-15 to create the GDS-12R, which increased the alpha from .76 to .81 [45]. The GDS-12R was found to have good internal consistency and test-retest reliability [45]. It is a self-report scale of depressive symptoms and uses a yes/no format. The scale measures how the person has felt during the previous week and usually takes 5 to 7 minutes to complete, making it ideal for older adults in residential facilities. Scores  $\geq 5$  are significant for depressive symptoms [46].

**Meaning in Life Questionnaire (MLQ)** will be used to measure MIL. Steger et al. MLQ [47] has two subscales which assess the presence of meaning (how much a person feels their life has meaning) and the search for meaning (how much a person strives to find meaning and understanding in their life) [48]. The two-subscale measure consists of 10 items on a 7-point Likert scale, ranging from 1-absolutely true to 7-absolutely untrue: five items for presence of meaning and five items for search for meaning. This questionnaire has been shown to have high convergent and discriminant validity and has been tested across age, gender, race, and national groups [47], [48]. The MLQ questionnaire does not have cut off scores like the Geriatric Depression Scale, but based on numerous studies, a score  $> 24$  indicates a person feels their life has meaning and purpose [48].

The GDS-12R and MLQ will be administered by the PI at three times; pre-test, post-test 1, and post-test 2. These measures will be administered orally to each participant and answers recorded by the PI on a tablet.

One open-ended feedback, qualitative, question will be asked of participants at post-test 2: "What did you think of the experience of participating in Life Story Book?" This question will be documented in writing with no names or ID numbers recorded.

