## **25.0 Data Management**

Data will be analyzed using IBM SPSS Version 25 [49] and a multivariate analysis of covariance (MANCOVA) will be performed. Descriptive analysis will be conducted to describe participants, including demographic characteristics and their functional status (ADL). Demographic variables will be assessed with t-tests for independent samples (continuous variables) and chi-squared (categorical variables) to determine baseline differences. Prior to conducting the main analysis, data will be evaluated to ensure that assumptions for multivariate tests are fulfilled, including normality, linearity, univariate and multivariate outliers, homogeneity of variance-covariance matrices, and multicollinearity. Data will be inspected for any errors in data entry and for any missing data. Any reasons for withdrawal from the study and the loss to follow-up will be recorded.

A one-way MANCOVA will be performed to test for differences between the experimental group (LSB) and the control group on the 2 outcome measures (GDS-12R and MLQ), while using pre-test scores as covariates. Main effects from pre-test to post-test in both groups will be examined. To look at long term effects, repeated t-tests will be conducted at post-test 2.

Thematic analysis of the qualitative question will be conducted by the research team to identify themes in the data concerning the experience of participating in LSB.

Only the research team will have access to the encrypted and password protected database on which the study information will be stored. All members of the research team will be trained in appropriate data management techniques and the importance of maintaining confidentiality of data. All data will be inputted by the PI and then independently reviewed for accuracy by another member of the research team.

Eligibility screeners, consent documents, and documentation for receipt of the completed LSB will contain participants names (not ID numbers), and they will be kept separate from all other study information in a locked filing cabinet in the PI's office (345A SOCW) until after the study where they will be scanned and kept on an encrypted and password protected file on SharePoint, and maintained by my faculty advisor.

The code book with the name and the ID number of the participant will be kept in a separate locked filing cabinet in SOCW room 333, and will be destroyed following data collection.

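### The MLQ anchors as printed run against the score's stated meaning and Hypothesis II, with no recode given, and the plan never says which MLQ score is analysed

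*Combined protocol and SAP*

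**What the plan says.** **Scale and direction.** Section 10.0 gives the MLQ ten items on a 7-point scale, "ranging from 1-absolutely true to 7-absolutely untrue: five items for presence of meaning and five items for search for meaning". It adds that the instrument has no cut-off scores of the kind the depression scale has, but that a score above 24 "indicates a person feels their life has meaning and purpose". Hypothesis II (section 1.0) is that the intervention raises meaning in life more than usual care does. The measures are read aloud, with "answers recorded by the PI on a tablet". The instruments are attachments and are not in the reviewed text.

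**Constructs.** The protocol separates two constructs. Presence is the degree to which someone experiences life as meaningful. The other subscale is defined as "the search for meaning (how much a person strives to find meaning and understanding in their life").

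**Analysis.** Section 5.0 reports "A power analyses for a MANOVA, with 2 groups and 2 dependent variables". Section 25.0 tests the groups "on the 2 outcome measures (GDS-12R and MLQ), while using pre-test scores as covariates", and adds: "To look at long term effects, repeated t-tests will be conducted at post-test 2". Section 9.0 (Study Endpoints) defines no efficacy endpoint that would say which MLQ score is meant.

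**The concern.** There are two separate gaps in one of the trial's only two outcomes.

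*Direction.* With 1 at the true end, a resident who strongly agrees that life has meaning gets the lowest score. The sentence about 24 and Hypothesis II both treat a high score as more meaning. Both can hold only if the items are recoded, and no recode is stated. A tablet form built from this paragraph, with results then read in the direction of the hypothesis, would report a benefit as a harm or a harm as a benefit. The planned inspection for data-entry errors would not by itself show this, because each entry would agree with the form.

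*Score.* Presence and search are described as different things: having meaning, and striving to find it. A single variable called MLQ could be either subscale or their sum. The three can give different results, and the choice stays open until the data are in hand.

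**Working it through.** **1. The plan's own figure and the number of outcomes.** Inputs from section 5.0: 2 groups, 2 dependent variables, N = 20, alpha .05, effect size .94, power 95%. With .94 entered as the MANOVA effect size f², noncentrality .94 × 20 and F df (2, 17), power is 95.2%, so the stated 95% reproduces with two dependent variables. (The .94 is labelled d, which is a separate matter.) With three dependent variables, power at N = 20 falls to 91.0% and 95% needs N = 23. The design therefore has GDS-12R and one MLQ variable.

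**2. Direction.** Inputs: anchors 1 to 7 and five items per subscale (section 10.0). Assumption: affirmatively worded items.
- A five-item score runs from 5 to 35, with midpoint 5 × 4 = 20.
- A score above 24 needs a mean item score above 24/5 = 4.8. As printed, that lies on the untrue side of 4, the opposite of the stated interpretation.
- The recode 8 - x on each item turns a five-item score S into 40 - S.

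**3. What a reversal does to the test.** If every item is reversed at every visit, post-test and pre-test MLQ both become 40 - S (80 - S for ten items). This is a linear change of one outcome and its covariate, so the MANCOVA statistic and p-value are unchanged. The adjusted group difference changes sign. At post-test 2, a two-sided t-test likewise keeps its p-value and changes sign.

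**4. Which score 24 refers to.** On ten items (range 10 to 70, midpoint 40), 24 is 24/10 = 2.4 per item, well below 4. On five items it is 4.8. The sentence therefore fits a five-item score better, and its wording resembles the definition of presence. The protocol does not say so.

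**5. Dilution if the ten-item sum is used.** Assumptions, none of them in the documents: equal subscale SDs (set to 1), an effect δ on presence, none on search, subscale correlation c. The sum has effect δ and SD √(2 + 2c), so the fraction of the standardised effect kept is 1/√(2 + 2c).

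| c | √(2 + 2c) | Fraction kept |
|---|---|---|
| -.3 | 1.183 | 85% |
| 0 | 1.414 | 71% |
| .3 | 1.612 | 62% |

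**6. False positives if the score is chosen after seeing results.** Simulation with no true effect, normal test statistics for presence and search with correlation c, their standardised sum, and two-sided .05 for each:

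| c | Presence or sum | All three scores |
|---|---|---|
| -.3 | 8.8% | 12.1% |
| 0 | 8.3% | 11.5% |
| .3 | 7.8% | 10.5% |

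These rates are for a stand-alone MLQ test, not for the joint MANCOVA.

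**7. Entering both subscales instead.** With N = 20, 2 groups, p outcomes and p pre-test covariates, error df = 20 - 2 - p and F df = (p, error df - p + 1). For p = 2: error df 16, F df (2, 15). For p = 3: error df 15, F df (3, 13). The second is not the two-variable design of section 5.0.

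**The case against.** **The items are not printed, and the attached form may hold the key.** This stands as a limit. The conflict rests on affirmative wording, which the definition of presence makes likely but does not prove, and a recode may be on the attachment. The claim can be made only of the reviewed text. Even so, a correct form would leave the body text at odds with itself.

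**A reversal would be noticed.** Section 2.0 calls meaning protective against depression, and section 25.0 checks linearity and multicollinearity. A reversed MLQ would tend to correlate positively with GDS-12R, and one person administers every questionnaire to at most 24 residents. Detection is plausible, but no step is aimed at it, and a correlation in so small a sample is weak evidence.

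**Presence is the obvious reading.** It fits best, and search is a poor candidate for an increase in meaning. That makes the fix easy, but it does not pre-specify the score, and section 25.0 says only MLQ.

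**Stronger readings that the documents do not support.** A reader might infer that the MLQ test is invalid; a whole-score reversal leaves its p-value alone. A reader might infer that residents would be misclassified at 24; no planned analysis uses that threshold. A reader might add three 5% tests and expect 15% false positives; the sum is determined by the two subscales, so the rate is lower. Nor does any passage suggest that the score will be picked after the fact.

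**Conclusion.** The point holds and should be fixed before the first pre-test.

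That the analysed score is unnamed is clear from the text and depends on no assumption about item wording. Its size is conditional: 62-85% of a presence effect retained if the sum is used (equal SDs, no search effect, c from -.3 to .3), and a false-positive rate of about 8-9% (presence or sum) to 10.5-12% (all three) for a stand-alone MLQ test only if the choice follows the results.

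On direction, the paragraph is wrong as written if the items are affirmative. The harm is a reversed sign for Hypothesis II, not an altered p-value, and it needs two steps: answers keyed as printed, and higher then read as more meaning. The documents do not show that either has happened or will. Swapped labels in the text may be the whole explanation.

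**What to change.** In section 10.0, correct the anchors, or state the recode (8 minus the item score, listing any item scored the other way) so that higher means more meaning. Check the tablet coding against the attached form before the first pre-test.

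In sections 10.0 and 25.0, name the five-item presence subscale as the single MLQ outcome, the MLQ pre-test covariate and the MLQ measure at post-test 2. Say that the value of 24 refers to that subscale. Report search descriptively.

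The cost is a few words in two sections and one check of the form. No new data are needed, and the two dependent variables of section 5.0 are kept. The downside is that search falls outside the confirmatory test.

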## **11.0 Setting**

An IRB modification will be submitted once the nursing homes' information and letters of cooperation are obtained.

The interventions will be conducted at the nursing homes.

## **12.0 Drugs or Devices**

N/A

## **13.0 Risks to Subjects**

We will be administering instruments regarding mood. Participants may experience mild psychological discomfort. The Life Story Book intervention may result in some temporary mild psychological discomfort while discussing the past. The instruments will be administered by a Licensed Master Social Worker. In addition, both RAs will be trained and supervised by the PI on skills for working with older adults-including gauging physical capabilities and the handling of disturbing memories.

An additional foreseeable risk of fatigue for participants may occur during the intervention. The plan for minimizing the fatigue risk is to let the participants, at the beginning of each visit, know that they can stop and rest at any time or may reschedule the session if they are too fatigued to continue. The research team will be extremely flexible and attentive as to adjusting intervention times, assessing for fatigue, being watchful for pain or other symptoms.

Participant risk will be further reduced by conducting the intervention in the NHs which are providing physical and psychological services to the participants.

Although every effort will be made to conduct the intervention in private, there is also the potential risk to the privacy for the participants as other residents or NH staff may hear the stories they are relaying.

There is a minimal risk of violations of confidentiality associated with all research studies. However, safeguards have been established to protect participant confidentiality.

Inconveniences for participants will be closely monitored. Scheduled visits will be done at the most convenient time for the participant with careful consideration of scheduled activities, i.e. meals, naps, medicine.

Residents are members of residential communities and their involvement in a study may have implications for other members of the community [31]. One way to address this is to provide a LSB toolkit that can be used by the NH to enable other residents the same opportunity to make their own LSB. A toolkit containing all of the essentials needed for making LSB and will be donated to each NH after the study is completed.

**FULL PROTOCOL TITLE:** The Effectiveness of Life Story Book on Depression and Meaning in Life for Mentally Alert Residents of Nursing Homes

## **14.0 Potential Benefits to Subjects**

Participants will receive a Life Story Book for participating, even if the participant ends participation before all data collection has finished. What has been recorded will be inserted into their own Life Story Book album. Participants will receive the benefit of having their own Life Story Book.

Furthermore, potential benefits participants may experience is lower depressive symptoms and increased meaning in life.

## **15.0 Provisions to Monitor Data to Ensure the Safety of Subjects**

This is a minimal risk study.

## **16.0 Withdrawal of Subjects**

Participants may withdraw from the study at any time without risk of loss of receiving a book, even if it is blank, or only partially full of their stories. Participants will receive their Life Story Book even if they are unable, or choose to stop participation, and/or not complete all measures. For example, if after one or two visits of sharing their life stories, a participant chooses, or is unable to complete the intervention, what has been shared will be transcribed and their LSB will be compiled and given to them.

Individuals whose health is compromised, per advice of NH medical staff, will be withdrawn from the study. The research team, if possible, will advise the participant and have some closure. If appropriate, a book will be given to them, even if it is blank.

## **17.0 Costs/Payments to Subjects**

There are no costs for participating. Participants will receive their own Life Story Book at no cost to them.

Participants will sign documentation to verify that they have received their LSB. This documentation will be kept in a locked file separate from all de-identified study data so that no identifying information could be linked back to participation in this study. (*Please see attached form*).

## **18.0 Compensation for Research-Related Injury**

N/A

## **19.0 Confidentiality**

Provisions will be made to protect all identifiable data in order to protect the privacy and maintain the confidentiality of all participants from recruitment to maintaining the data. These provisions will include the confidentiality of residents who did not meet the eligibility criteria; de-identification of each participant with a study number; a database created and files secured with passwords used only by the research team; components of the study data will be kept in a locked file cabinet; the research team will be well trained in how to maintain participant

**FULL PROTOCOL TITLE:** The Effectiveness of Life Story Book on Depression and Meaning in Life for Mentally Alert Residents of Nursing Homes

confidentiality; and the research team will have completed the required CITI training on ethical conduct of research. To ensure privacy, written agreements between the research team and the participants will be signed to ensure that no stories will be included in their LSB that do not have the express permission of the participants. The LSB will belong to the participant and any information or stories shared will not be disclosed to families or staff to protect the participant. (*Please see attached*).

**Paper Documentation of Screeners, Study Instruments and Receipt:** Eligibility screeners, consent documents, and documentation for receipt of the completed LSB will contain participants names (not ID numbers), and they will be kept separate from all other study information in a locked filing cabinet in the PI's office (345A SOCW). The code book with the name and the ID number of the participant will be kept in a separate locked filing cabinet in SOCW room 333, and will be destroyed following data collection. Completed study instruments will only contain the participants' ID number and will be kept on an encrypted and password protected file on the UH SharePoint site. Any data or documentation relating to this study will not be accessed by anyone but the research team.

**Each participant will have a participant folder** generated on a password protected file on UH OneNote where their transcriptions, notes, photos and/or memorabilia will be stored. The research team will edit and organize the text into a cohesive narrative while adding any photos to the narrative. The research team will make every effort to ensure that the facts are correct and verified with the participants with a first draft before a final printing of their LSB. If the participant would like to have an electronic copy in addition to their book, the research team will copy their LSB folder onto a USB flash drive and give that to the participant with their book.

**Audio Recordings:** The LSB intervention visits will be audio recorded and members of the research team will transcribe the interviews. A professional transcriber will be hired, as needed, to help with the transcriptions. After transcription, the audio files will be destroyed.

**Intervention Notes:** LSB intervention notes, that each RA has written, will be used to add to, or supplement, interview audio recording transcripts. Once these notes have been added to, or used to verify transcriptions, the notes will be destroyed.

**Scanned Photos and/or Memorabilia:** All photos and/or memorabilia will be scanned onto a microSD card which has the participant's ID number on it. This microSD card will be uploaded onto the password protected file folder of the participant on the UH OneNote site. The microSD card will then be wiped clean.

**Qualitative Question:** The answers from the one open-ended qualitative question will be documented in detailed notes and recorded onto a spreadsheet with no identifiable information.

**Video recorded and/or photographed for media:** There will be a presentation of the results of the study for all participants, nursing home residents, family members, and staff. Participants who would like to be identified as participants and video recorded and/or photographed will have

**FULL PROTOCOL TITLE:** The Effectiveness of Life Story Book on Depression and Meaning in Life for Mentally Alert Residents of Nursing Homes

the option to indicate their agreement on a supplemental consent form.

**20.0 Provisions to Protect the Privacy Interests of Subjects**

Participants will be provided with some examples of the *Life Review and Experiencing Form* questions as part of the informed consent process; in addition to the purpose of the

study and the necessity of disclosing some personal information. This will be clearly explained as part of the consent process. Participants will be informed that only the research team will have access to the LSB intervention transcripts and survey instruments. Participants will also be informed that they can refuse to answer any question or withdraw from the study at any time, without penalty, and without giving a reason for withdrawing from the study.

All survey instruments will be administered by the PI, a licensed master social worker who has experience working with older adults in nursing homes. The LSB intervention will be conducted by two social work/medical professionals who will be provided training, by the PI, for working with older adults in nursing homes. In addition, participants can ask questions about their participation in the research process at any time.

